$$Age_{transf.} = \left(\frac{Age\ at\ onset}{100}\right)^{-2} \qquad DxDelay_{transf.} = \left(\frac{DxDelay}{10}\right)^{-\frac{1}{2}} + \ln\left(\frac{DxDelay}{10}\right)$$

$$\Delta FRS_{transf.} = (\Delta FRS + 0.1)^{-\frac{1}{2}} \qquad VC_{transf.} = \left(\frac{VC}{100}\right)^{-1} + \left(\frac{VC}{100}\right)^{-\frac{1}{2}}$$

$$\Delta FRS_{transf} = \left(48 - FRS_{screening}\right) \div DxDelay$$

14. APPENDIX 4: SAS CODE

Mixed Model Repeated Measure

The following is example SAS syntax for producing least squares estimates, for the MMRM analysis:

```
proc mixed data=ALSFRS_LONG method=reml;
  class ID TRTRND(ref="0") STADCARE(ref="3") CHANGE(ref="<1")
TIME(ref="baseline");
  model DELFRS = TIME VALUEBL CHANGE STADCARE TIME*TRTRND TIME*VALUEBL TRP
  TIME*TRP / ddfm=kr solution;
  repeated TIME / type=UN subject=id;
  lsmeans trtrnd*TIME /cl pdiff=control('0' '5')cl;
  run;</pre>
```

where id is the subject identifier, trtrnd is the randomized treatment arm, stadcare is a factor variable for the SoC stratification group at baseline, change is the amount of change in the subject's ALSFRS-R score during the Screening Period, time is the categorical variable for study visit, Valuebl is the baseline ALSFRS-R score, TRP represents the TRICALS risk profile at baseline, and the response variable DELFRS is the change from baseline in ALSFRS-R score.:

ANCOVA with Multiple Imputation

SAS code for the ALSFRS-R endpoint at 24 weeks:

```
proc mi data = ALSFRS_DATA out = ALSFRS_DATA_OUT
    seed = 20221219 nimpute = 100 noprint;
    class trtrnd stadcare change sex;
    var trtrnd Valuebl change stadcare sex age trp
    ALSFRS_R_4 ALSFRS_R_8 ALSFRS_R_12 ALSFRS_R_16 ALSFRS_R_20 ALSFRS_R_24;
    fcs reg(ALSFRS_R_4 ALSFRS_R_8 ALSFRS_R_12 ALSFRS_R_16 ALSFRS_R_20
    ALSFRS_R_24);
    run;
```

The next set of code performs the analyses for the ALSFRS-R 24-week endpoint:

```
proc reg data=ALSFRS_DATA_OUT utset=outreg covout noprint;
  model ALSFRS_24 = trtrnd Valuebl change stadcare TRP;
  by _Imputation_;
  run;
```

This step will combine the results:

```
proc mianalyze data=outreg;
  modeleffects Intercept trtrnd Valuebl change stadcare TRP;
  run;
```

Pattern Mixture Model

The strategy implemented to carry out the control-based PMM assumes that all other variables, except ALSFRS-R, with missing data are first imputed using the FCS approached outlined in the previous sensitivity analysis, with 100 imputation datasets. These data are stored in DATAIN_IMP0, which contains a variable _Imputation_ to distinguish between multiple copies of the original input data. In the next step missing ALSFRS-R at the first time point will be imputed (the first time-point that has some missing data). To use the control-based imputation

method, the starting dataset will be separated into two separate datasets: DATAIN_IMP1, containing all Placebo subjects and those subjects from the PTC875 arm that have values at timepoint 1 missing; and DATAIN_REST1, containing the remainder of the subjects from the PTC875 arm who have ALSFRS-R scores available at this time point.

Create a variable VISIT1 where it is equal to 1 if ALSFRS-R is available at this visit and 0 if it is missing.

```
Data DATAIN_IMP1 DATAIN_REST1;
  set DATAIN_IMP0;
  if trtrnd = 1 and VISIT1 = 1 then output DATAIN_REST1;
  else output DATAIN_IMP1;
  run;
```

Next, use PROC MI to impute missing data at the first timepoint with missing data, based on the model estimated exclusively from control subjects with non-missing values at time-point 1. The following code assumes that Week 4 contains the first missing data from the ALSFRS-R outcome dataset.

```
Proc mi data= DATAIN_IMP1 out=DATAIN_REG_IMP1 nimpute=1 seed=1001;
    class trtrnd stadcare change sex;
    by _Imputation_;
    var trtrnd Valueb1 change stadcare sex age trp ALSFRS_R_4;
    monotone reg(ALSFRS_R_4);
    run;
```

Next, combine all the data into one dataset.

```
Data DATAIN_IMP1_COMB;
  set DATAIN _REST1 DATAIN_REG_IMP1;
  run;
```

Repeat the above steps for the second timepoint with missing data for ALSFRS-R. Dataset DATAIN_IMP1_COMB will be used for input to the next PROC MI call, but first, separate it into two datasets: DATAIN_IMP2, containing all Placebo subjects and those subjects from the experimental arm that have values at second timepoint missing; and DATAIN_REST2, containing the remainder of the subjects from the PTC875 arm. Create a variable VISIT2 where it is equal to 1 if ALSFRS-R is available at the second timepoint with missing data and 0 if it is missing. The below code assumes that this will be at Week 8.

```
Data DATAIN_IMP2 DATAIN_REST2; set DATAIN_IMP1_COMB;
    if trtrnd = 1 and VISIT2 = 1 then output DATAIN_REST2;
    else output DATAIN_IMP2;
    run:
```

Next use PROC MI to impute missing data at time-point 2 based on the model estimated exclusively from Placebo subjects with non-missing data at time-point 2.

```
Proc sort data= DATAIN_IMP2; by _Imputation_; run;
proc mi data=DATAIN_IMP2 out=DATAIN_REG_IMP2 nimpute=1 seed=1002;
    by _Imputation_;
    var trtrnd Valuebl change stadcare sex age trp ALSFRS_R_4 ALSFRS_R_8;
    monotone reg(ALSFRS_R_8);
    run:
```

Re-assemble the data back into a single dataset containing all subjects:

```
data DATAIN IMP2 COMB;
```

```
set DATAIN_REST2 DATAIN_REG_IMP2;
run;
```

Repeat the same procedure until ALSFRS-R is imputed at all timepoints.

The next set of code performs the analyses for the ALSFRS-R 24-week endpoint as for the FCS multiple-imputation approach, assuming that there were six timepoints at which there were missing data in the ALSFRS-R dataset:

```
proc reg data= DATAIN_IMP6_COMB utset=outreg covout noprint;
  model ALSFRS_24 = trtrnd Valuebl change stadcare TRP;
  by _Imputation_;
  run;
```

This step will combine the results:

```
proc mianalyze data=outreg;
  modeleffects Intercept trtrnd Valuebl change stadcare TRP;
  run;
```

Survival Analysis

The following is sample code for producing a Kaplan-Meier survival plot:

```
proc lifetest data=survdata plots=survival(cl cb=hw test atrisk);
   time time*status(0);
   strata trtrnd / test=logrand adjust=sidak;
   run;
```

where time is the time of event or censoring, status is the variable indicating censored (1) or not censored (0), i.e., death observed, trtrnd is the treatment allocation variable. The following sample code runs a Cox regression model:

```
proc phreg data=survdata atrisk plots(cl)=(survival cumhaz);
  class trtrnd stadcare TRP(ref='B');
  STRATA stadcare change;
  model time*status(0)= trtrnd Valuebl / ties=breslow rl;
  hazardratio trp;
  run;
```

where time is the time of event or censoring, status is the variable indicating censored (1) or not censored (0), i.e., death observed, and trtnd is the treatment allocation variable.

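### Appendix 4 of both SAPs defines the survival status variable the opposite way from its own code, and the Cox code is not the model that Section 5.7 (Part A) or Section 5.4 (extension) specifies

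*SAP*

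**What the plan says.** **Text.** Section 5.7 of the Part A SAP and Section 5.4 of the extension SAP (Parts B and C) specify the same analysis. It is a Cox model stratified by screening loss of ALSFRS-R points and by Yes/No background ALS therapy, with baseline ALSFRS-R and the TRICALS risk profile as covariates and Breslow ties. It estimates the hazard ratio of PTC857 against placebo, and subjects not known to have died are censored at the date last known alive. Section 5.1 of the Part A SAP treats TRICALS as continuous.

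**Status coding.** Appendix 4 of each SAP explains the variable after the Kaplan-Meier code and again after the Cox code: "status is the variable indicating censored (1) or not censored (0), i.e., death observed". The Part A Kaplan-Meier call reads "time time*status(0"), and both Cox calls and the extension Kaplan-Meier call also use status(0).

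**Part A Cox code.** It is introduced with "The following sample code runs a Cox regression model". The CLASS statement begins "class trtrnd stadcare TRP(ref='B", the STRATA statement names stadcare and change, the MODEL statement is "model time*status(0)= trtrnd Valuebl / ties=breslow rl", and the last request is "hazardratio trp".

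**Extension Cox code.** This block is not called sample code. CLASS lists trtrnd, stadcare and TRP. MODEL contains trtrnd, change and stadcare. There is no STRATA statement.

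**The concern.** An appendix of code is what a programmer is most likely to copy. Here it conflicts with the section it implements, and neither SAP says in general which prevails.

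The analysis matters for three reasons. Survival is a listed secondary endpoint. Section 3.3.3 of the Part A SAP makes the hazard ratio the population-level summary for survival time. Section 5.1 says that CAFS is hard to interpret and that the Section 5.7 results will describe the survival difference. With few deaths expected, the covariates and strata should be fixed unambiguously beforehand, not settled while the program is being repaired.

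The erratum to the Part A SAP corrects a redundant mention of TRICALS in Section 5.1 and does not touch Appendix 4.

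**Working it through.** The plan states no figure to reproduce. The check sets text against code and then sizes the consequence.

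**1. Status.** In PROC LIFETEST and PROC PHREG the value in brackets after the status variable is the censored value. This is SAS syntax, not a statement in the documents. The sentence gives 1 = censored and 0 = death. The code gives 0 = censored. They contradict each other in both SAPs.

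**2. Cox model.**

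| Element | Text (5.7 and 5.4) | Part A code | Extension code |
|---|---|---|---|
| Strata | screening loss; background therapy | both, as strata | none; both are covariates |
| Baseline ALSFRS-R | covariate | in MODEL | absent |
| TRICALS | covariate | in CLASS with reference B; absent from MODEL | in CLASS; absent from MODEL |
| Screening loss | categories | stratum | not in CLASS, so a single numeric term |
| Ties | Breslow | Breslow | no option given |
| Hazard ratio | treatment | HAZARDRATIO names trp | no HAZARDRATIO statement |

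Part A agrees on strata, baseline ALSFRS-R and ties; it fails on TRICALS and on the hazard ratio requested. The extension code fails on stratification and on both covariates. I do not count its missing ties option, because Breslow is the PHREG default.

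**3. Precision available in Part A.** Inputs from Section 1.5 of the Part A SAP: 205 and 102 ITT1 subjects, with 24-week survival of 96.5% and 95%.

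- Expected deaths: 205 × 0.035 = 7.2 and 102 × 0.05 = 5.1, total 12.3.
- Hazard ratio implied by those rates: ln(0.965)/ln(0.95) = 0.69. No document plans a hazard ratio; this is derived from the CAFS survival assumptions.
- SE(ln HR) = √(1/7.175 + 1/5.1) = 0.579.
- 95% CI factor: exp(1.96 × 0.579) = 3.11, giving 0.22 to 2.16 around 0.69.

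**4. Effect of leaving TRICALS out (illustrative).** I simulated 300 trials per setting (246 to 263 usable) with 205/102 subjects, six strata, exponential deaths and Breslow ties, and compared the treatment hazard ratio from the Section 5.7 model with that from the Part A code. The TRICALS slope (log hazard per unit), its SD and the strata mix are assumptions that the documents do not supply.

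| Slope | SD | Median factor | 95th percentile |
|---|---|---|---|
| 0.5 | 0.5 | 1.02 | 1.15 |
| 0.5 | 1.0 | 1.05 | 1.28 |
| 1.0 | 0.5 | 1.05 | 1.30 |
| 1.0 | 1.0 | 1.13 | 1.56 |

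On the same 24-week data, the text model against the extension code gave medians of 1.06 to 1.14. That is not the 52- or 160-week horizon, so the size of the extension discrepancy is not established.

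**The case against.** The text can fairly be read as governing. Both Part A survival blocks and the extension Kaplan-Meier block are labelled sample code. Section 5.1 points to Section 5.7, not to the appendix, and Sections 5.7 and 5.4 are complete and consistent with each other. The Part A Cox block would need rewriting in any case: it sets a letter as the reference level of a numeric score and requests a hazard ratio for a variable not in the model. No route to a silently wrong Part A hazard ratio is shown. All of this stands and keeps the severity low. It does not remove the contradiction, and the extension Cox block lacks the sample label.

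Three stronger readings are tempting.

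- **Deaths will be analysed as censored.** This would happen only if the dataset followed the sentence while the code ran as printed; 307 − 12.3, about 295 subjects, would then count as events. Nothing in the documents says the dataset is coded that way, and the Section 5.7 table of deaths and censored subjects would probably expose it.
- **The hazard ratio will print upside down.** Neither Cox block sets a treatment reference level. If the software took PTC857 as reference, 0.69 would print as 1/0.6946 = 1.44. That depends on a software default the documents do not state, and the output would label the comparison.
- **Part A is still committed to a three-level therapy factor.** The appendix describes stadcare as the standard-of-care stratification group, but Section 3.5 of the Part A SAP already says the Section 5 analyses use the binary form.

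**Conclusion.** The point holds as a mismatch between text and code in both SAPs. The status sentence contradicts status(0). The Part A Cox code departs from Section 5.7 on TRICALS and on the hazard ratio requested. The extension Cox code, the worse case, departs from Section 5.4 on stratification and both covariates.

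It is a low-severity correction. The body text is right, survival is not among the endpoints in the Section 4.6 sequence, CAFS is unaffected, and no wrong reported result has been demonstrated. In Part A the likely numerical effect of leaving out TRICALS is small beside sampling error. That judgement rests on the planning survival rates and the assumed TRICALS slope and spread; for the extension no size can be given. The conclusion itself needs only the text comparison and the SAS meaning of the bracketed value.

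**What to change.** In both SAPs, before the Part A treatment codes are opened:

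1. State that 1 = death and 0 = censored, and keep status(0).
2. Replace the Cox code with `CLASS trtrnd(ref='0'); STRATA stadcare change; MODEL time*status(0) = trtrnd valuebl trp / ties=breslow rl;`, with TRP continuous and stadcare defined as the Yes/No background-therapy variable.
3. Delete the HAZARDRATIO statement for trp, or replace it with one for trtrnd.
4. Say that Section 5.7 (Part A) and Section 5.4 (extension) govern wherever the appendix code differs.
5. Remove the test option from the Kaplan-Meier code ("strata trtrnd / test=logrand adjust=sidak"). Neither section specifies a log-rank test, so correcting the spelling alone would keep an unplanned test. If one is wanted, add it to the text first.

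The cost is one or two sentences and a few lines of code in each SAP. Data collection, the primary analysis and the testing sequence do not change.

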15. APPENDIX 5. MAPPING ALSFRS-R TO KING'S STAGE

The King's clinical staging criteria for ALS (Balendra 2014) is defined as a count of involved central nervous system (CNS) regions (Stage 1, 2 or 3), requirement for gastrostomy or noninvasive ventilation (Stage 4) and death (Stage 5).

Stage	Definition
1	Functional involvement of one CNS region (symptom onset)
2	Functional involvement of two CNS regions
3	Functional involvement of three CNS regions
4	Need for gastrostomy (4A) or non-invasive ventilation (4B)
5	Death

- 1. Bulbar region is involved: If the subject dropped any points on any of the three ALSFRS-R questions regarding speech (question 1), salivation (question 2) or swallowing (question 3).
- 2. Upper limb region is involved: If the subject dropped any points on either of the two ALSFRS-R questions regarding hand function, which are handwriting (question 4) and ability to cut food and handle utensils (question 5A).
- 3. Lower limb region is involved: If the subject dropped any points on the ALSFRS-R question regarding ability to walk (question 8).
- 4. Stage 4A attained: If question 5B is answered instead of question 5A, which is only answered by patients without a gastrostomy.
- 5. Stage 4B reached: If a patient scored 0 points on question 10 or less than 4 points on question 12.

16. REVISION HISTORY

The following list summarizes the major changes incorporated into Version 2.0 of the SAP from Version 1.0.

Section	Description of Change	Brief Rationale
SAP	The version number and date were updated	Update
	throughout.	'
	The intent of the SAP was changed from a	
	description of all the analyses for the whole study (all	
	Parts) to a description of the analyses pertaining to	
	the double-blind treatment period (Part A). A	
	description of all analyses for the long-term extension	
	periods and entire study are now described in a	
	separate SAP	
	Editorial and administrative revisions (e.g.,	
	typographical errors, punctuation, tenses,	
4.0	abbreviations) were incorporated to provide clarity.	Analysis of the Language
1.2	Objectives for the Long-Term Extension periods	Analyses of the Long-term
	(Parts B and C) were removed	extension periods are described
1.3.2	Added Opposedow conduciate	in a separate SAP
1.3.2	Added 2 secondary endpoints	Following Protocol amendment 6.0
1.3	Long-Term Extension periods (Parts B and C)	Analyses of the Long-term
1.5	endpoints removed	extension periods are described
	enupoints removed	in a separate SAP
1.5	Description of sample-size updated following change	Update
1.0	in the primary endpoint as recommended by the FDA.	Opadio
1.6	Removed extraneous unblinding details that are not	Update
	necessary in the SAP, as they are described in the	Opusio
	protocol	
2.4	Criteria for removal of subjects from the ITT	Update
	population, to form the per-protocol population is	•
	added.	
2.6	Added more text with examples of major protocol	Update
	deviations (PD), and definition of PDs	
3.2	Treatment compliance section removed, because it's	Update
	described in Section 4.8	
3.3	The whole section has been updated to reflect FDA	Update
	feedback, to change the primary efficacy endpoint	
	from change from baseline in ALSFRS-R to subject	
	ranks based on the combined assessment of function	
	and survival (CAFS). Text updated to provide more clarity	
4.8	Treatment compliance is more clearly defined, and	Update
4.0	formula added.	Opuate
	Extent of exposure is more clearly defined.	
4.9	Visit Windows for The Early Termination Visit and	
	Unscheduled Visits were added.	
5	The whole section has been updated to reflect FDA	Update
	feedback, to change the primary efficacy endpoint	
	from change from baseline in ALSFRS-R to CAFS.	Joint model requires making
	Text updated to provide more clarity.	unknown assumptions regarding
	T Joint Model (Shared parameter) analysis removed.	the change in function overtime.
5.6	Additional subgroup analyses of interest added	Update

Section	Description of Change	Brief Rationale
6.2.1	Additional incidence rate analyses specified	Update
6.2.2	Additional summaries to evaluate differences in AEs that are indicative of disease progression added	Update
6.2.3	Additional summaries to evaluate disproportionate rate of disease progression by treatment	Update
6.8	Weight change categories added Breast Imaging and Pregnancy summaries specified	Update
6.9	Subgroup Analyses for Safety specified	Update

ERRATUM

STATISTICAL ANALYSIS PLAN FOR THE DOUBLE-BLINDED TREATMENT PERIOD (PART A) OF PTC857-CNS-001-ALS

VERSION NUMBER: 2.0, DATED: 25 SEPTEMBER 2024

ISSUE DATE: 29 OCTOBER 2024

The purpose of this erratum is to correct a typographical error in the Statistical Analysis Plan for Part A of Study PTC857-CNS-001-ALS, version 2.0, dated: 25 SEPTEMBER 2024.

The first paragraph of Section 5.1 contains redundant text implying that the TRICALS variable would be incorporated into the model twice (as a covariate and as a main effect), instead of solely intended as a covariate. The following table displays the paragraph with the extraneous text marked in strikethrough font.

The primary efficacy variable, subject ranks based on the combined assessment of function and survival (CAFS) after 24 weeks of treatment will be performed using an analysis of covariance model (ANCOVA) following multiple imputation. The estimand framework described in Section 3.3.1 will be used. The ANCOVA model will contain the following main effects: treatment (PTC857 or placebo), the amount of change in the subject's ALSFRS-R score during the Screening Period (<1, 1-2, or 3-4-points total loss), TRICALS risk profile (continuous), use of Approved Background Therapy for ALS (Yes [either riluzole, edaravone, or sodium phenylbutyrate/taurursodiol], No). Baseline ALSFRS-R score (continuous) and The TRICALS risk profile (continuous) will be included as covariates.

STATISTICAL ANALYSIS PLAN

A Phase 2, Randomized, Double-Blind, Placebo-Controlled, Parallel Study to Assess the Efficacy, Safety, Tolerability, PK and Biomarker Effects of PTC857 in Adult Subjects with Amyotrophic Lateral Sclerosis (CARDINALS)

FOR THE

OPEN LABEL LONG-TERM EXTENSION PERIOD (PART B), CONTINUED LONG-TERM EXTENSION PERIOD (PART C) AND ENTIRE STUDY PERIOD (PARTS A, B AND C POOLED) OF PTC857-CNS-001-ALS

VERSION 1.0

SOC	System Organ Class
TEAE	Treatment-Emergent Adverse Event
TESAE	Treatment-Emergent Serious Adverse Event
TRICALS	TRICALS is the largest European research initiative to find a cure for ALS
ULN	Upper Limit if Normal
WHO DD	World Health Organization Drug Dictionary

1. INTRODUCTION AND OVERVIEW

The purpose of this statistical analysis plan (SAP) is to provide a description of the statistical methods and procedures to be implemented for data analysis of the open-label long-term extension periods (Parts B and C) and the entire study period (where applicable), for PTC857-CNS-001-ALS, a Phase 2 randomized trial.

This document is based on the final protocol amendment version 6.0, dated 14 JUNE 2024 and has been developed, reviewed and approved prior to the database lock. Any changes from the planned analysis as described in the protocol for PTC857-CNS-001-ALS and its amendments (as applicable) are detailed here, and any differences described here supersede the analysis presented in the protocol. Any additional analyses conducted to supplement the planned analyses and any deviations from the planned analyses described in this SAP will be documented in the Clinical Study Report (CSR).

1.1. Study Design

Brief description of the Study Design

This is a Phase 2, randomized, double-blind, placebo-controlled, parallel-group study to assess the effects of PTC857 (also known as utreloxastat) in adult male and female subjects diagnosed with amyotrophic lateral sclerosis (ALS). Eligible male and female subjects aged between 18 and 80 years will be enrolled in this study. The study consists of 5 periods: Screening, Treatment (Part A), LTE (Part B), Continued LTE (Part C), and Follow Up. During the open-label extension periods (Parts B and C), subjects remain blinded to the original treatment allocation in Part A.

Approximately 340 subjects who meet the inclusion and exclusion criteria will be randomized in a 2:1 ratio to receive PTC857 (250 mg BID) or matching placebo using a central randomization process. The randomization will be stratified for the 2 stratification factors:

- 1. Amount of change in ALSFRS-R score during the 8-week Screening Period by points total loss:
 - a. <1,
 - b. 1-2,
 - c. 3-4,
 - d. >4 points total loss
- 2. Use of edaravone, sodium phenylbutyrate/taurursodiol, or neither for the treatment of ALS at Screening as standard-of-care therapy:
 - a. Edaravone
 - b. Sodium phenylbutyrate/taurursodiol
 - c. Neither edaravone nor sodium phenylbutyrate/taurursodiol

[figure not shown]
Before protocol amendment version 4.0, dated 31 OCTOBER 2022, the second stratification factor above (treatment for ALS at baseline) was based on use of riluzole alone (i.e., the following two levels: on riluzole therapy for ALS and not on riluzole therapy). Protocol amendment 4.0 opened the study to allow for randomization of subjects who were taking other

treatments for ALS if approved in their region of participation, specifically edaravone and sodium phenylbutyrate/taurursodiol if their treatment was considered stable at screening. In protocol amendment 4.0 the original riluzole stratification groups (on riluzole therapy vs. not on riluzole therapy) would be amalgamated, and randomization would be based on edaravone, sodium phenylbutyrate/taurursodiol, and neither, as indicated above.

After completion of the 24-week double-blind treatment phase, all subjects will be offered the opportunity to enter the optional 28 weeks long-term extension (LTE) Period of the study. Those who choose to enter the LTE Period will sign an additional informed consent form (ICF) and start open-label treatment with PTC857 250 mg BID. Those who choose not to enter the LTE Period will stop treatment, and a telephone follow-up visit will be conducted 4 weeks (±3 days) after the last dose of study treatment. At the end of the LTE Period, those who choose not to enter the Continued LTE Period will stop treatment, and a Telephone Follow-Up Visit will be conducted 4 weeks (±3 days) after the last dose of study treatment. Subjects who enter the Continued LTE Period (Part C) will continue treatment for an optional additional 108 weeks. All subjects will be treated with open-label PTC857 (250 mg BID) during the Continued LTE Period. Subjects will remain blinded to their original treatment from the Treatment Period (Part A). At the end of this period, a Telephone Follow-Up Visit will be conducted 4 weeks (±3 days) after the last dose of study treatment. Results from the Treatment Period (Part A), the LTE Period (Part B), and the Continued LTE Period (Part C) will be reported separately. The scheduled study visit assessments are presented in Section 11 (Appendix 1).

Total duration of the individual participation will be approximately 172 weeks, including a screening period of 8 weeks mandatory in duration, a double-blind treatment period of 24 weeks, a long-term open-label extension period of 28 weeks, a continued long-term extension period of 108 weeks, and a follow up period of 4 weeks. A subset of approximately 36 subjects from select sites participating in the PK sub-study will participate in serial blood sampling to characterize the PK of PTC857 in subjects with ALS. The study schema is shown below.

Figure 1: Study Design

